Eligibility will be determined through participant report, chart review, and communication with CMHC clinician/psychiatrist, and this will be completed by the PI and research coordinator.

HIC 1606017928

9. Risks: Describe the reasonably foreseeable risks, including risks to subject privacy, discomforts, or inconveniences associated with subjects participating in the research.

Bupropion and Bupropion/Naltrexone combination:

Small increased risk of depression, suicidal ideation, and suicide: Due to the small increased incidence of depression, suicidal ideation, attempts, and completed suicides in people having taken Naltrexone and Bupropion separately (but not in combination studies), we will monitor this risk using the Columbia Suicide Severity Rating Scale as well as regular check-ins /mood evaluations with the study psychiatrist through study participation. If, during screening or throughout the trial, a patient indicates suicidal thoughts or plans, they will be further assessed by a clinical team member or the study doctor, who will then refer the patient to their regular clinician, CMHC acute services or the YNHH emergency room, as indicated.

Risk of seizure: Bupropion can cause seizures. The risk is decreased by extended-release formulations. The extended-release formulation of bupropion that will be used in this study has a seizure incidence of 0.1%. The risk of seizure is dose-related. The incidence of seizure in patients receiving the Bupropion Naltrexone combination in clinical trials was approximately 0.1% vs 0% on placebo. The risk of seizures is also related to patient factors, clinical situations, and concomitant medications that lower the seizure threshold. We will exclude patients with any history of seizures.

Increase in Blood Pressure and Heart Rate: Bupropion alone or bupropion naltrexone combination can cause an increase in systolic and/or diastolic blood pressure as well as an increase in resting heart rate. In clinical practice with other bupropion-containing products, hypertension, in some cases severe and requiring acute treatment, has been reported. Blood pressure and heart rate in all patients, will be closely monitored throughout the trial.

Hepatotoxicity: Cases of hepatitis and clinically significant liver dysfunction has been observed with naltrexone alone at doses 10 to 12 times the study dose. No hepatotoxicity has been reported at or twice the study dose nor with the combination pill.

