- b. If children are involved, what is the investigator's assessment of the overall risk level for the children participating in this study? N/A
- c. Data Safety Monitoring Plan

This is a moderate risk study. Although the naltrexone and bupropion dosages we use are at and below the FDA approved dose and these drugs have been safely used in this particular population in the

HIC 1606017928

literature, the potential exists for anticipated and/or unanticipated adverse events, serious or otherwise, to occur since it is not possible to predict with certainty the absolute risk in any given individual. The principal investigator is responsible for monitoring the data, assuring protocol compliance. [name], an experienced psychiatrist, will act as a safety officer and will be conducting safety reviews with the investigators twice a year. During the review process, the safety officer will evaluate whether the study should continue unchanged, require modification/amendment, continue or close to enrollment. Either the principal investigator, the safety officer, the Human Investigation Committee (HIC) or Human Subjects Committee (HSC) have the authority to stop or suspend the study or require modifications.

This protocol presents moderate risks to the subjects and adverse events or other problems are not anticipated. In the unlikely event that such events occur, serious and unanticipated and related adverse events or unanticipated problems involving risks to subjects or others will be reported in writing within 48 hours to the HIC or HSC (using the appropriate forms from the website). The investigator will apprise fellow investigators and study personnel of all adverse events that occur during the conduct of this research project in accordance with Federal and Institutional regulations.

Attribution of Adverse Events:

Adverse events will be monitored for each subject participating in the study and attributed to the study procedures/design by the principal investigator according to the following categories:

- a.) Definite:** Adverse event is clearly related to investigational procedures(s)/agent(s).
- b.) Probable:** Adverse event is likely related to investigational procedures(s)/agent(s).
- c.) Possible:** Adverse event may be related to investigational procedures(s)/agent(s).
- d.) Unlikely:** Adverse event is likely not to be related to the investigational procedures(s)/agent(s).

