- e.) Unrelated:** Adverse event is clearly not related to investigational procedures(s)/agent(s).

The following scale will be used in grading the severity of adverse events noted during the study:

- 1. Mild adverse event**
- 2. Moderate adverse event**
- 3. Severe**

In addition to grading the adverse event, the PI will determine whether the adverse event meets the criteria for a Serious Adverse Event (SAE). An adverse event is considered serious if it:

- 1. is life-threatening**
- 2. results in in-patient hospitalization or prolongation of existing hospitalization**
- 3. results in persistent or significant disability or incapacity**
- 4. results in a congenital anomaly or birth defect OR**
- 5. results in death**
- 6. based upon appropriate medical judgment, may jeopardize the subject's health and may require medical or surgical intervention to prevent one of the other outcomes listed in this definition, or**
- 7. adversely affects the risk/benefit ratio of the study**

HIC 1606017928

An adverse event may be graded as severe but still not meet the criteria for a Serious Adverse Event. Similarly, an adverse event may be graded as moderate but still meet the criteria for an SAE.

Plan for reporting serious AND unanticipated AND related adverse events, anticipated adverse events occurring at a greater frequency than expected, and other unanticipated problems involving risks to subjects or others to the HIC or HSC:

The investigator will report the following types of adverse events to the HIC(IRB), and the FDA (as appropriate): a) serious AND unanticipated AND possibly, probably or definitely related events; b) anticipated adverse events occurring with a greater frequency than expected; and c) other unanticipated problems involving risks to subjects or others. These adverse events or unanticipated problems involving risks to subjects or others will be reported to the HIC (IRB), and the FDA (as appropriate) within 5 calendar days of it becoming known to the investigator, using the appropriate forms found on the website.

The safety officer ([name]) will conduct a review of all adverse events upon completion of every study subject. The principal investigator will evaluate the frequency and severity of the adverse events and determine if modifications to the protocol or consent form are required at that time.

- d. For multi-site studies for which the Yale PI serves as the lead investigator: N/A

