The Naltrexone Bupropion combination was evaluated for safety in five double-blind placebo controlled trials in 4,754 overweight or obese patients (3,239 patients treated with THE NALTREXONE BUPROPION COMBINATION and 1,515 patients treated with placebo) for a treatment period up to 56 weeks. The majority of patients were treated with The Naltrexone Bupropion combination 32 mg/360 mg total daily dose. In addition, some patients were treated with other combination daily doses including naltrexone up to 50 mg and bupropion up to 400 mg. All subjects received study drug in addition to diet and exercise counseling. One trial (N=793) evaluated patients participating in an intensive behavioral modification program and another trial (N= 505) evaluated patients with type 2 diabetes. In these randomized, placebo-controlled trials, 2,545 patients received The Naltrexone Bupropion combination 32 mg/360 mg for a mean treatment duration of 36 weeks (median, 56 weeks). Baseline patient characteristics included a mean age of 46 years, 82% women, 78% white, 25% with hypertension, 13% with type 2 diabetes, 56% with dyslipidemia, 25% with BMI greater than 40 kg/m², and less than 2% with coronary artery disease. Dosing was initiated and increased weekly to reach the maintenance dose within 4 weeks. In The Naltrexone Bupropion combination clinical trials, 24% of subjects receiving The Naltrexone Bupropion combination and 12% of subjects receiving placebo discontinued treatment because of an adverse event. The most frequent adverse reactions leading to discontinuation The Naltrexone Bupropion combination were nausea (6.3%), headache (1.7%) and vomiting (1.1%).

The most commonly reported side effects associated with taking The Naltrexone Bupropion combination in completed clinical trials of overweight and obese individuals were: Nausea (32.5%), Constipation (19.2%), Headache (17.6%), Vomiting (10.7%), Dizziness (9.9%), Insomnia (9.2%), Dry Mouth (8.1%), Diarrhea (7.1%), Anxiety (4.2%), Hot flush (4.2%), Fatigue (4.0%), Tremor (4.0%).

In placebo-controlled clinical trials with the Naltrexone Bupropion combination for the treatment of obesity in adult patients, no suicides or suicide attempts were reported in studies up to 56 weeks in duration (equivalent to bupropion doses of 360 mg/day). In these same studies, suicidal ideation was reported by 3 (0.20%) of 1,515 patients treated with placebo compared with 1 (0.03%) of 3,239 treated with the Naltrexone Bupropion combination.

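### The monitoring plan gives the safety officer no prompt notice of a serious event and, separately, leaves unclear whether known risks count as anticipated for reporting

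*Combined protocol and SAP*

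**What the plan says.** **The safety officer.** Section V.11.c appoints a psychiatrist who "will be conducting safety reviews with the investigators twice a year" and who, like the PI, the HIC and the Human Subjects Committee (HSC), may stop or suspend the study. Later in the same section the officer "will conduct a review of all adverse events upon completion of every study subject". The PI's assessment of whether the protocol or consent form needs changing is tied to that same review. Completion is not defined. The investigator must also inform co-investigators and study personnel of all adverse events, but no time limit is set and the officer is not named.

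**Anticipated or not.** The section first accepts that "the potential exists for anticipated and/or unanticipated adverse events, serious or otherwise, to occur". One paragraph later it says "This protocol presents moderate risks to the subjects and adverse events or other problems are not anticipated", and treats such events as unlikely. Section V.9 lists seizure, suicidality, raised blood pressure, opioid withdrawal and hypoglycemia among the risks. On seizure it says "Bupropion can cause seizures" and "The extended-release formulation of bupropion that will be used in this study has a seizure incidence of 0.1" percent. Section VI.A.2 gives nausea at 32.5% on the combination and reports that "24% of subjects receiving The Naltrexone Bupropion combination and 12% of subjects receiving placebo discontinued treatment because of an adverse event".

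**Reporting.** Rule (a) covers "serious AND unanticipated AND possibly, probably or definitely related events". Rule (b) covers anticipated events that occur more often than expected, and rule (c) covers other unanticipated problems. All three lead to the HIC and, where appropriate, the FDA, within 5 calendar days. An earlier paragraph sets 48 hours, to the HIC or HSC, for serious, unanticipated, related events and for unanticipated problems.

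**The concern.** The officer holds stopping authority but is told of events on a calendar or end-of-subject schedule, not when they happen. Meanwhile other subjects continue on, or start, the same drugs. If 40 subjects enroll evenly over 2 to 2.5 years (an assumption; the documents give only a 3-year project), 13 weeks brings in 40/130 × 13 = 4.0 to 40/104 × 13 = 5.0 new subjects.

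Separately, rules (a) and (b) depend on whether an event is anticipated, and the plan answers that question in two ways. The serious events most likely to matter here, such as a seizure, are those already named as risks. For these events the route to the HIC is least certain.

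**Working it through.** The plan states no figure to reproduce. The check sets the review triggers and reporting rules side by side, with simple arithmetic.

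**Inputs.** Treatment lasts 16 weeks (Section V.3). Enrollment is 40 (Section VII.1), randomized 1:1, so about 20 per arm. Seizure incidence is 0.1% (Section V.9). Officer reviews are half-yearly and at subject completion (Section V.11.c).

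**1. Wait until the officer's review.** The two triggers run in parallel, so the wait is the shorter of the time to completion and the time to the next half-yearly review.

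- *Subject stays in to week 16.* The upper limit is 16 − w weeks for an event in week w: 15 weeks (105 days) at week 1, 13 weeks (91 days) at week 3 and 8 weeks (56 days) at week 8. A half-yearly review may fall sooner.
- *Subject stops early and this does not count as completion.* Only the half-yearly review applies. With evenly spaced reviews (assumption), the wait is at most 365.25/2 = 183 days, about 26 weeks, and averages 365.25/4 = 91 days if events fall evenly.
- *Subject stops early and this does count as completion.* Review follows at once.

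Section VI.A.2 itself says the combination should be discontinued and not restarted after a seizure, so the meaning of completion matters in exactly that case. As a rough guide to how many subjects it could affect, applying the discontinuation rates in Section VI.A.2 gives 0.24 × 20 + 0.12 × 20 = 7.2 of 40. Those trials ran up to 56 weeks and their placebo arm had no bupropion, so this is illustrative only. It counts all adverse-event stops, serious or not.

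**2. Which reporting rule covers a drug-related seizure?**

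- If Section V.9 defines what is anticipated, the seizure falls outside rule (a) and can reach the HIC only under rule (b).
- If the statement that events are not anticipated governs, the seizure falls inside rule (a).

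Rule (b) needs a reference rate and a threshold. At 0.1%, the expected count in 40 subjects is 40 × 0.001 = 0.04, and the chance of at least one seizure is 1 − 0.999^40 = 3.9%. One seizure in 40 is 2.5%, 25 times the quoted rate, so a case for rule (b) is easily made. Yet the exact 95% interval for 1/40 runs from 0.06% to 13.2% and includes 0.1%, so the opposite case can be made too. The documents contain rates, but the monitoring plan does not adopt them as the reference or say what counts as an excess.

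**3. Are the two defects linked?** No. The anticipated/unanticipated sort governs reports to the HIC and FDA. The officer reviews all adverse events however they are classified. Correcting the wording would not bring the officer's review forward, and prompt notice to the officer would not settle the HIC route.

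**4. Clocks.** Serious, unanticipated, related events carry both a 48-hour and a 5-calendar-day limit in the same section. The documents do not say which applies.

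**The case against.** The strongest case against the point is that oversight does not depend on the officer. The PI monitors throughout, with physician checks weekly for four weeks and then monthly (Section VI.A.5). The HIC can stop the study, and a seizure can reach it within days under rule (a) or, arguably, rule (b). The officer may count as study personnel who must be told of all events, and completion may simply mean the end of each subject's participation. All of this stands as a limit on the point. None of it supplies a timed, named notice to the officer or a definition of completion.

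A reader might also infer four stronger claims, which the documents do not support:

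- *The contradictory wording causes the officer's delay.* It does not; step 3 shows that the two are separate.
- *A serious event of a known kind escapes all independent review for months.* The HIC may learn of it within days. The documents do not describe the officer as independent; the half-yearly reviews are held with the investigators.
- *The adverse events of subjects who leave early are never reviewed.* The half-yearly review still covers them, so the effect is delay, not omission.
- *The plan has no expected frequencies.* Sections V.9 and VI.A.2 give several. What is missing is their adoption as the reference for rule (b), and a threshold.

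**Conclusion.** The point holds as two separate defects in Section V.11.c, each worth correcting because correction is nearly free.

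1. Under the stated triggers, the safety officer may not see a week-3 serious event for up to 13 weeks if the subject stays in, or for up to about 26 weeks if the subject stops early and that is not completion. These are maxima. They assume evenly spaced half-yearly reviews, per-subject reviews held as each subject finishes, and no informal notice to the officer. They describe the officer's review only, not the PI's or the HIC's.
2. The statement that adverse events are not anticipated contradicts the section's own earlier text and the risks and rates in Sections V.9 and VI.A.2. It leaves open whether a serious event of a known kind is reported under rule (a) or only under rule (b), which has no designated reference.

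The two reporting clocks are a further contradiction in the same text. None of this touches the primary weight analysis.

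**What to change.** In Section V.11.c:

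- Require notice to the existing safety officer of every serious event judged at least possibly related, anticipated or not, when the PI learns of it, with a documented decision to continue, modify or pause.
- Change the per-subject review trigger to completion or early discontinuation.
- Delete the statement that adverse events are not anticipated. Designate the Section V.9 risks as the anticipated list for rules (a) and (b), with the rates in Sections V.9 and VI.A.2 as the reference for rule (b). State what counts as exceeding a rate, since known risks would then reach the HIC through rule (b). Say so where no rate is given (opioid withdrawal and hypoglycemia, for example), and note that the registration trials of the combination excluded antipsychotic users (Section V.2).
- Reconcile the 48-hour and 5-calendar-day limits. Which one applies is for the sponsor and the HIC to settle.

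The cost is an edit to one section, a few extra notifications, and short reviews by an officer already appointed. No new staff, visits or study procedures are needed.
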